# 12. POTENTIAL BENEFITS TO SUBJECTS

There may be direct and/or indirect benefits of study participation. Participants are receiving a brief intervention that addresses a transdiagnostic factor that may reduce opioid use. This intervention can be used for both participants who are not engaged in treatment and for participants who are engaged in treatment, it may augment current services. Dissemination of the findings from the study will contribute to the extant literature, provide data to guide a larger trial, and may contribute to reducing loneliness and opioid use, and understanding how reductions in loneliness impact opioid use.

# 13. COSTS FOR PARTICIPATION

None

Page 11 of 20

# 14. PAYMENT FOR PARTICIPATION

Participants will receive compensation for their participation in the study. The compensation amount will be based on the schedule that follows:

| Baseline Assessment                        | \$40 |
|--|------|
| Completing first 3 sessions within 4 weeks | \$20 |
| Mid-intervention assessment                | \$20 |
| Post-treatment Assessment (w/in a week)    | \$40 |
| 30-day Assessment                          | \$30 |
| 60-day Assessment                          | \$30 |

Therefore, the total compensation for completing all the study components would be \$180. Payments will be made following each study procedure listed above. Participants who do not complete the entire study for any reason, will receive compensation for the components that were completed per the above schedule of payments.

# 15. SUBJECT WITHDRAWALS

- The only anticipated circumstances under which subjects will be withdrawn by the investigator from the research without their consent would be if they were lost to contact and if new information about them suggested that they did not meet eligibility criteria.
- Subjects may withdraw from the research themselves at any time and/or completes some but not all study procedures. We will utilize all data collected.
- If we have not met our target 'n' for study completers, to the extent that funding and staff time allow, we will replace subjects withdrawn from the study.

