# 5. SUBJECT POPULATION

We will nationally recruit 125 adults with OUD for this randomized clinical trial. We estimate that our screen failure rate will be approximately 10-30%. We estimate attrition from the consent and baseline assessment to the end of the 2-month follow-up to be approximately 20%.

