## 9. STUDY PROCEDURES

Screening: The project coordinator will screen by phone following a script. Potential participants will provide verbal consent to complete the screening measures. Those individuals meeting eligibility who are interested in participating will be scheduled for a telehealth-based appointment to go over Consent, complete eConsent, and conduct a baseline assessment. Assessments and Intervention: Participants will be enrolled following consent and will complete the baseline assessment. Following the baseline assessment, participants will be randomized to condition (control or experimental) by a computer-generated algorithm. Participants will schedule a convenient time for their telehealth-based intervention sessions. Mid-treatment, posttreatment, and 30- and 60-day post-treatment follow-up assessments will also be conducted by telehealth. Participants will be paid \$40 each for the baseline and post-treatment assessment, \$20 for the mid-treatment assessment and \$30 each for the 30-day and 60-day follow-up assessments. Participants will also be paid \$20 for completing the first 3 sessions within 4 weeks. The posttreatment assessment will also include an exit interview for participants to describe acceptability of the intervention. All assessments and interventions will be conducted via Zoom (including toll-free phone option) or phone. If requested, participants will be sent a letter indicating study activities completed.

Randomization: We will randomize at the participant level using block randomization in groups of 4. All demographic and outcome variables will be assessed for baseline equivalency. Any between-group baseline differences will be controlled for statistically in all subsequent analyses with baseline differences being defined here as any absolute standardized mean difference (Cohen's d) greater than or equal to .15.

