## 17. DATA ANALYSIS PLAN

Aim 1: To assess the efficacy of CBT-L's impact on loneliness, negative affect and the quality and quantity of social interactions among individuals with OUDs. Outcomes variables will include loneliness, negative affect, and the quality and quantity of social interactions. We will conduct mixed regression modeling with condition, time, time by condition interactions, and relevant covariates included as predictors.

Aim 2: To assess the cognitive, affective, and behavioral mechanisms of the effect of CBT-L on opioid use trajectories. Outcome variables for this aim will include opioid use and craving. Exploratory mediation analysis will be conducted to examine whether CBT-L reduces opioid use trajectories and whether these reductions occur due to reductions in loneliness and/or negative affect and social interaction quality/quantity.

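### Investigator withdrawal for lost contact or suspected ineligibility is not limited to the period before randomisation, and the plan does not commit to attempting later assessments or analysing everyone as assigned

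*Combined protocol and SAP*

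**What the plan says.** Section 15 (Subject Withdrawals) has three bullets.

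- The first gives the only circumstances in which the investigator expects to withdraw someone from the research without consent: "if they were lost to contact and if new information about them suggested that they did not meet eligibility criteria". It sets no time limit and does not mention randomisation.
- The second covers people who withdraw themselves and people who complete only part of the procedures. It adds: "We will utilize all data collected".
- The third applies if a target number of completers, not given in that section, has not been reached: "to the extent that funding and staff time allow, we will replace subjects withdrawn from the study".

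Section 9 fixes the order of events. Screening is by phone, then come consent and baseline, and then: "Following the baseline assessment, participants will be randomized to condition (control or experimental) by a computer-generated algorithm". Mid-treatment and post-treatment assessments follow, and the "30- and 60-day post-treatment follow-up assessments will also be conducted by telehealth". Section 14 pays for each component separately: "Participants who do not complete the entire study for any reason, will receive compensation for the components that were completed".

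For Aim 1, Section 17 specifies "mixed regression modeling with condition, time, time by condition interactions, and relevant covariates included as predictors". It names no analysis set. Section 5 expects "attrition from the consent and baseline assessment to the end of the 2-month follow-up to be approximately 20" per cent.

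**The concern.** Withdrawal here is from the research as a whole, so following the rule as written ends outcome collection. Most loss of contact will occur during the six weekly sessions or the 60 days after them, when the person has already been randomised. Ineligibility that comes to light in that period also falls after randomisation.

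Two things are at stake. First, a mixed model can use a partial record but cannot use an assessment that nobody attempted. Someone unreachable during treatment may answer at 30 or 60 days, and someone judged ineligible may be fully reachable throughout. Second, with no analysis set named, the plan does not settle in advance whether a randomised person later judged ineligible counts in the primary comparison. Replacement restores a count of completers, not the missing outcomes.

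Discretion after randomisation deserves care because late information need not surface equally in the two arms. The first CBT-L session takes a history of the onset, severity and impact of loneliness, and loneliness is an entry criterion. The control sessions cover topics such as diet, exercise and sleep. Section 9 states blinding for the coordinator's assessments; it does not say whether whoever decides on withdrawal is blinded. This shows how an imbalance could arise, not that one will.

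**Working it through.** The plan gives no figure for investigator withdrawals, so the check is mainly a comparison of sections, with some bounding arithmetic.

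**Does the rule reach randomised people?** Section 15 sets no time limit, and Section 9 places randomisation straight after baseline. Yes. Some ineligibility may still be caught earlier: participants are enrolled at consent, and Table 1 repeats the NIH Toolbox loneliness scale at baseline.

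**What can one withdrawal cost?** The scheduled assessments are baseline, mid-treatment, post-treatment, 30-day and 60-day, which makes 5. Those after randomisation number 5 − 1 = 4. One person is 1/63 = 1.6% of the CBT-L arm or 1/62 = 1.6% of the control arm.

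**How many could there be?** Section 5 gives about 20% attrition, and Sections 1 and 4 give 125 randomised (63 + 62).
- All losses: 125 × 0.20 = 25, leaving 125 − 25 = 100 completers.
- Investigator withdrawals are part of those losses, so at that rate they lie between 0 and 25.
- Section 5 counts attrition from consent and baseline. It is treated here as counted from randomisation, which directly follows.

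**What is already protected?** The sentence on using all data sits in the bullet that also covers partial completion, which describes someone lost to contact midway. Together with a mixed model, it weighs against discarding data in hand. It says nothing about seeking further data, and a model does not define who enters it.

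**Can the bias be sized?** If a share f of one arm is missing at an assessment and those missing differ from those observed by g, the observed mean of that arm is off by f × g. The documents give neither f by arm and reason nor g, so neither size nor direction follows.

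**What does keeping ineligible people cost?** Suppose k of the 63 in CBT-L are ineligible and gain nothing (an assumption). The effect shrinks by k/63:
- k = 1: 1.6%
- k = 2: 3.2%
- k = 3: 4.8%

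**Assessment payments after randomisation:** 20 + 40 + 30 + 30 = $120, already within the $180 schedule in Section 14.

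**The case against.** The strongest reply is that the plan already does most of the work. It uses all data collected, from partial completers too; its model accepts incomplete records; and it pays for each assessment completed. Retention is on the weekly meeting agenda (Section 9), and reports to the monitoring officer must cover biases in attrition (Section 16, Data and Safety Monitoring Plan). For people truly lost, a promise to keep trying recovers little. Late-found ineligibility may be rare, because screening and a repeat of the loneliness scale come before randomisation. The study also calls itself a pilot.

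Most of this stands, and it limits the point to outcomes not yet collected and to who is analysed. None of it commits the trial to attempting remaining assessments or to analysing by assigned arm.

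Three stronger readings are not supported:
- A reader might infer that withdrawn people's data will be thrown away. The sentence on using all data points the other way.
- A reader might infer that investigator withdrawal for ineligibility should be barred after randomisation. Withdrawal from the research also covers the sessions, and eligibility includes age and understanding of consent, so a flat bar would reach beyond follow-up and analysis.
- A reader might infer that replacement will push the number randomised well above 125. Section 15 gives no number for the completer target and limits replacement by funding and staff time. No such number can be derived, and it would not measure harm from the withdrawal rule.

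**Conclusion.** The point holds in a limited form. As written, the withdrawal rule can end outcome collection for randomised participants, at a cost of up to 4 of 5 assessments each, and the available text contains no commitment to attempt those assessments or to analyse everyone as assigned. Data already in hand are largely protected. At the stated attrition, about 25 of 125 is a ceiling on such withdrawals, not an estimate. A reader might infer a bias in favour of CBT-L; the documents support neither a direction nor a size.

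This is a cheap improvement worth making, not a flaw that invalidates the design. The absence is claimed only for the text available: part of the document between Sections 2 and 4 and part at the end of Section 9 could not be seen. Sections 15 and 17, where these rules would normally stand, were available. The missing number for the completer target is a detail to fill in, not a separate defect.

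**What to change.** In Section 15 (Subject Withdrawals) add:

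*After randomisation, where valid consent stands, loss of contact or later-found ineligibility does not end outcome follow-up; each remaining scheduled assessment through 60 days is attempted.*

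In Section 17 add:

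*All randomised participants are analysed in their assigned arm using all available data; exclusion for ineligibility, based only on pre-randomisation facts, is a sensitivity analysis. Added participants are newly randomised and displace no one from the analysis.*

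This wording concerns outcome follow-up and analysis only. It sets no rule on stopping sessions. It leaves invalid consent, a participant's own withdrawal and the monitoring officer's safety decisions as they are.

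The cost is a few sentences and some further contact attempts. The assessment payments are already scheduled, whereas a replacement can cost the full $180 plus six sessions. The statistical price is the slight dilution shown above, and the sensitivity analysis would show how much the result depends on it.

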# 16. PRIVACY AND CONFIDENTIALITY OF SUBJECTS AND RESEARCH DATA

With respect to confidential data collection, all project data will be collected by trained research interviewers using IRB approved data collection instruments. In addition, research interviewers and interventionists will receive on-going supervision through the course of the project. All data will be stored in locked file cabinets and password protected databases and will be accessible only by appropriate research personnel. All subject data will be identified by a unique number. Subject identifiers (e.g., name, address, telephone number) will be stored separately from research data and linkable through a unique identification number. All study personnel will receive mandatory education in human subjects' protection. All data will be used for research purposes only, and will not be revealed without the participants' written consent unless to protect individual's immediate safety. All paper data will be kept in locked files in a locked study office. Computerized data will be stored in databases on a secure, password protected server that is regularly backed up. As an added protection, NIH funded studies are covered by a Federal Certificate of Confidentiality.

All research and clinical information obtained is kept confidential unless the subject is an immediate danger to him/herself or to others. Subject well-being will be monitored throughout the study. If the clinical information obtained in the course of research assessments pertains to patient safety (e.g., intent to harm one's self or others) then, to promote safety, confidentiality will not be maintained, and appropriate treating professionals will be informed. During crisis situations, this clinical information may be provided to other clinicians (or family members) in order to facilitate appropriate treatment and minimize the risks of self-harm or harm to others. This information may include the subject's medical history, financial and social resources, and history of suicidal behavior, if known. Confidentiality is the ethical and/or legal right that information, such as research data, will be held

Page 12 of 20

secret and safeguarded from disclosure unless consent is provided permitting disclosure.

# 15. DATA / SAMPLE STORAGE FOR FUTURE USE

We will share data with other researchers and use widely used measures that will facilitate harmonization with other research. However, the data sharing agreement involves sharing only deidentified data with other investigators and the use of data-sharing agreements that provide for: (1) a commitment to using the data only for research purposes and not to identify any individual participant; (2) a commitment to securing the data using appropriate computer technology; and (3) a commitment to destroying or returning the data after analyses are completed. A Data Use Agreement (DUA) will be made with The Ohio State University. The DUA will be for sending the de-identified dataset electronically. [name] will not have access to any data.

# 16. DATA AND SAFETY MONITORING PLAN

Data Safety. To ensure safety of participants in the study proposed and validity and integrity of data collected, the PI ([name]) will oversee all data and safety monitoring functions and the research team will be advised that he will be the primary contact overseeing these activities. The PI and the research team will meet regularly to monitor study progress and discuss the implementation of monitoring procedures. He will also meet regularly with the research coordinator and to review monitoring procedures and ensure all efforts are being taken to minimize risks to participants. The PI will have an independent Data Safety Monitoring Officer (DSMO) to help monitor safety issues. The DSMO will be at least an Assistant Professor at University of Rochester who is independent of this study and has substantial randomized clinical trial experience for individuals with substance use disorder or mental health condition. As indicated below, the PI will track all negative outcomes and incidents as well as conduct interim data analysis every 12 months after the study has started. The study design will be significantly modified (and even screening stopped) on the suggestion of the DSMO that the study is creating potential harm to our participants.

The PI will regularly oversee all aspects of the study, including participant recruitment, informed consent, data collection, management, and analysis, as well as regularly assess the risk/benefit ratio associated with participation in the study. All research staff will participate in an intensive training to help them understand the importance of reducing the risk for participants and learning how to recognize and report any AE or SAE. SAEs may include: death, hospitalization due to worsening psychiatric symptoms or suicidal ideation, or all life threatening or disabling/incapacitating events among research participants. AEs may include, but are not limited to: physical injuries, worsened physical or mental health, or inadvertent disclosure of confidential research information.

If an SAE occurs, the PI will immediately contact the DSMO and IRB, followed by a written report in 24 hours. He will make a decision whether there is sufficient evidence to suspend data collection, allow for further IRB review, modify the protocol, or make other changes to reduce potential risk to participants. The study will resume based on agreement of the PI, an IRB member, and the DSMO. In the event that an AE that is not an SAE is reported to the PI, the PI will discuss the event with the DSMO. Immediate evaluation will occur to determine if any extra steps can be taken to minimize the likelihood of that type of AE occurring again. If changes can be made, a report/amendment will be written and submitted to the DSMO and IRB.

Page 13 of 20

As part of a standard practice, the PI will supervise the implementation of one audit within 4 months after study recruitment with subsequent audits each year of the materials collected and produced as part of the study to ensure proper confidentiality and compliance with ethical principles, including informed consents, electronic medical record documentation, questionnaire data, and to make sure that the research staff are following established protocols. The PI will provide an annual summary report of all AEs to the IRB and the DSMO as part of the annual review. If no adverse events have occurred, the report will state, "No adverse events affecting human participants have occurred during this project year."

Data Monitoring. To ensure adequate participant recruitment and enrollment, each week, the PI will discuss the current number of participants contacted, screened, and enrolled from each site and compare those numbers to the expected based on our preliminary data. If after the first 4 months, it appears we are not reaching our expected number of participants, the PI will discuss potential barriers/obstacles and solutions with the DSMO. Discussions regarding recruitment and enrollment will continue at each meeting with the DSMO to ensure proper implementation of the study.

Data Safety Monitoring Officer. The purpose of the DSMO is to review protocols and consent documents for this study, monitor safety issues throughout the study, provide an overview of the quality of the accumulating data, and provide guidance on interim analyses and stopping rules. The DSMO will have no direct involvement in the study or conflict of interest with the research team conducting the clinical trial. The DSMO will have expertise in: research and monitoring atrisk research participants; research in longitudinal clinical trials with using cognitive-behavioral intervention; and research expertise with individuals using substances. The DSMO responsibilities will include:

- (1) Review, provide approval/disapproval, and provide suggestions to protocols and consent documents.
- (2) Monitor, provide suggestions, and report on ethical issues regarding protection of human subjects, and advise on ethical issues regarding AEs. The DSMO will coordinate with the PI to report to the IRB any unanticipated problems involving risk. The DSMO will provide potential solutions or other appropriate actions (e.g., altering inclusion/exclusion criteria, changing consent documents).
- (3) Ensure appropriate balance between clinical care, safety, and patient confidentiality.
- (4) Monitor data regarding effectiveness. The DSMO will review outcome data for outcomes by treatment condition. If differences in results between conditions appear to be clinically significant, the DSMO will review whether the clinical trial should continue with or without further enrollment of new participants.
- (5) Monitor and review any data relevant to quality control.

The PI will convene semi-annually with the DSMO for the duration of the study. The meetings will be held in-person or via video teleconference. The DSMO and PI will decide on the format of the meetings. Additional meetings will be held on the recommendation of the DSMO and meeting logistics will be based on clinical urgency and the availability of the DSMO. The PI will submit reports to the DSMO a week prior to the scheduled meeting. Reports will

Page 14 of 20

include all data up to and including 2 weeks prior to the reporting deadline (except for SAEs, which are to be reported within 24 hours of an event). For each meeting at which the study is to be considered or monitored, the PI will present an overall progress statement containing the assurance that the PI has considered the clinical trial's progress and that there is/is not evidence of safety issues that should be addressed by the DSMO. The reports will also include information related to problems in recruitment, biases in attrition, biases with respect to AEs, or other operational problems that affect the integrity of the study. At the additional request of the DSMO, interim analyses will be conducted to determine whether the emerging findings may lead to a discussion of discontinuing the trial early.

The DSMO will be kept apprised of all SAEs and AEs on an ongoing basis and will decide whether individual patients should be removed from the protocol. Although research staff, under the PI's supervision, are able to take whatever immediate action is necessary to safeguard the welfare of individual patients, the DSMO will be called on whenever possible to make decisions as a result of a SAE. There may be rare instances where some unanticipated situations occur that may affect participant welfare. In these situations, the IRB or the DSMO may be contacted to help resolve the situation.

